**Methodology (Continued):**

In addition, the following will be conducted during the study as noted below:

- Results of QoL and work productivity questionnaires (IBDQ, EQ-5D, WPAI) at Baseline, Week 8, and Weeks 16, and 52/Early Termination.
- Serum for measurement of ABT-494 concentrations at Week 2, Week 4, Week 8, Week 12, Week 16, Week 20, Week 28, Week 36, Week 44 and Week 52/Early Termination.
- A serum pharmacodynamics sample will be drawn at Baseline, Week 8, Week 16 and Week 52/Early Termination.
- Endoscopic evaluations using SES-CD, confirmed by central reader, will be done during Screening, Week 12 or Week 16, and Week 52/Early Termination. The Week 12 or Week 16 endoscopy will not be performed if a subject discontinues the study prior to Week 8. In addition, if a subject prematurely discontinues from the extension phase of the study before or at Week 28, the endoscopy at the Early Termination Visit will not be required. Biopsy to confirm diagnosis (during Screening) or to rule out dysplasia/malignancy may be performed during the same time points as the endoscopy specified above.
- Stool samples for measurement of fecal calprotectin during Screening, Week 4, Week 16, Week 28 and Week 52/Early Termination Visit and at Unscheduled Visits resulting in dose change.
- Results of Abdominal Pain Rating Scale (0 – 10 scale) evaluating Abdominal Pain Intensity will be collected at Baseline, Week 12 and Week 16. (Note: this is an additional pain scale to the daily pain assessment that is collected as part of the CDAI).
- An optional serum for evaluation of biomarkers at Baseline and Week 16.
- An optional whole blood mRNA sample will be drawn at Baseline and Week 16.
- An optional whole blood pharmacogenetic sample will be drawn at Baseline.
- An optional biopsy for Gene expression sub-study will be collected during colonoscopy at/during Screening, and at Week 12/16 for approximately 80 subjects in the study.

Throughout the study, subjects will only be allowed to change the dosage of CD-specific concomitant medications as specified below:

- Starting at Week 2, subjects who are taking corticosteroids at Baseline must have their steroid dose tapered.
- Aminosalicylates dose must remain unchanged for the entire study period.
- MTX dose must remain unchanged for the entire study period.

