5.2 Variables Used for Stratification of Randomization

At Baseline, subjects will be randomized in a 1:1:1:1:1:1 ratio to receive one of the six treatment groups (double-blind ABT-494 induction doses or matching placebo).

The following are the treatment groups:

Group 1: ABT-494 3 mg BID

Group 2: ABT-494 6 mg BID

Group 3: ABT-494 12 mg BID

Group 4: ABT-494 24 mg BID

Group 5: ABT-494 24 mg QD

Group 6: Placebo

The randomization at Baseline will be stratified by endoscopic disease severity (SES-CD < 15 and \geq 15), prior anti-TNF use (naïve and experienced), and by participation in the substudy of the gene expression in intestinal biopsies (Yes and No). As part of the randomization at Baseline, subjects will be randomly assigned (1:1) to have their follow-up ileocolonoscopy done at Week 12 or Week 16.

At Week 16, subjects who have completed the induction period will be re-randomized in a ratio of 1:1:1 to one of the three double-blinded doses of ABT-494 3 mg BID, 6 mg BID or 12 mg BID. The re-randomization will be stratified by dose received during the first 16 weeks, and overall response (responder versus non-responder) at Week 16. The

subjects who were re-randomized at Week 16 to ABT-494 24 mg QD prior to Protocol Amendment 2 will continue to receive the same double-blind dose until Week 52/PD.

Overall response consists of both Endoscopic response and Clinical response. The central reader endoscopic score will be used for calculating the Endoscopic response for the evaluation of the efficacy endpoints. However, for stratification re-randomization, the endoscopic score at baseline from central reader and the endoscopic score at Week 12 or Week 16 from site local reader will be used in order to determine response status.

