All videotaped colonoscopies will undergo central review. One primary central reviewer will evaluate the videotaped colonoscopies and provide the SES-CD scores to Parexel. A second central reviewer will adjudicate between the investigator's and the central reviewer's SES-CD scores if there is discrepancy (more than 10% difference) in total SES-CD score. The adjudicator will select the final SES-CD score that he/she most agrees with from those provided by the investigator and the central reviewer, and this final SES-CD score will be entered into the study database and be used for the study's efficacy analyses. If there is no discrepancy between the investigator and the central reviewer, that central reviewer's score will be entered into the study database and serve as the SES-CD score to be used for the study's efficacy analyses.

If there is a missing SES-CD individual variable in the SES-CD score that serves as the SES-CD score for the study's efficacy analyses (for all variables except the "Presence of Narrowing" variable), the following imputation rules will be applied:

If the same individual variable is:

- Missing at both Baseline and Week 12 or 16: the missing value will be imputed as zero at both time points, and no change will be assumed.
- Present at Week 12 or 16 but missing at Baseline: the missing Baseline value will be imputed based on the value given at Week 12 or 16, and no change will be assumed.
- Present at Baseline but missing at Week 12 or 16: the missing Week 12 or 16 value will be imputed based on the value given at Baseline and no change will be assumed.

If there is a missing SES-CD "Presence of Narrowing" individual variable in the SES-CD score that serves as the SES-CD score for the study's efficacy analyses, the following imputation rules will be applied:

If the Presence of Narrowing individual variable is:

- Missing at both Baseline and Week 12 or 16: the missing Presence of Narrowing individual variable will be imputed as zero and no change will be assumed.
- Present at Week 12 or 16 but missing at Baseline: the missing Baseline value will be imputed based on the individual variable given at Week 12 or 16 and no change will be assumed.

However, if there is a Baseline individual variable (for any SES-CD subscore) for intestinal segments proximal to (above) the segment with the missing Presence of Narrowing individual variable, the maximum imputed value for the missing Presence of Narrowing individual variable will be 2.

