- Present at Baseline but missing at Week 12 or 16: the missing Week 12 or 16 value will be imputed based on score given at Baseline and no change will be assumed.

However, if there is a Week 12 or 16 individual variable is present for intestinal segments proximal to (above) the segment with the missing Presence of Narrowing variable, the maximum imputed value for the missing Presence of Narrowing individual variable will be 2.

(Gastrointestinal anatomy places the ileum proximal to the right colon, which is proximal to the transverse colon, which is proximal to the sigmoid and left colon, which is proximal to the rectum.)

A sensitivity analysis (Worst Case Imputation) will be performed by imputing all missing Baseline individual variables as '0' and all missing Week 12 or 16 variables as '3' except the Week 12 or 16 Presence of Narrowing individual variable. At Week 12 or 16, the worst values for Presence of Narrow individual variable will be 2 for Rectum, Sigmoid and Left Colon, Transverse Colon, and Right Colon, and 3 for Ileum.

If a subject only has Baseline SES-CD, and no post-Baseline SES-CD, all Baseline missing individual variables will be imputed as zero.

Isolated Ileal Crohn's Disease at Baseline

Isolated Ileal Crohn's disease at Baseline is defined as all individual variables for Rectum, Sigmoid and Left Colon, Transverse Colon, and Right Colon are zero at Baseline and subscore for ileal ≥ 4 . If any of the individual variables is missing or not zero, this subject is classified as Not Isolated Ileal Crohn's disease at Baseline.

Definition of Endoscopic Remission

SES-CD ≤ 4 and at least two point reduction versus Induction baseline and no subscore > 1 in any individual variable.

Definition of Endoscopic Response

SES-CD at least 25% reduction from Induction baseline.

Definition of Clinical Remission

Average daily stool frequency ≤ 1.5 and not worse than baseline AND average daily abdominal pain ≤ 1.0 and not worse than Induction baseline.

Definition of Clinical Response

Average daily stool frequency at least 30% reduction from Induction baseline and average daily abdominal pain not worse than Induction baseline OR average daily abdominal pain at least 30% reduction from Induction baseline and average daily stool frequency not worse than Induction baseline.

Definition of Remission

Remission at Week 16 is defined as both Endoscopic remission at Week 12/16 AND Clinical remission at Week 16.

Definition of Response

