- The proportion of subjects who achieve $> 50\%$ reduction from Baseline in SES-CD or endoscopic remission at Week 12/16.
- The proportion of subjects who achieve modified clinical remission at Week 16 among subjects with an average daily SF ≥ 4.0 or average daily AP ≥ 2.0 at Baseline.

For categorical efficacy endpoints for Induction Period, the pairwise comparisons for the difference in proportions of subjects between treatment groups and placebo group will be analyzed using the CMH test adjusted for Crohn's disease severity (SES-CD < 15 , ≥ 15) at Baseline. Additionally, the CMH-based 95% confidence interval for the difference in proportions will be provided. The 95% confidence interval for the difference in proportions within each Crohn's disease severity (SES-CD < 15 , ≥ 15) at Baseline category will be calculated based on normal approximation.

The non-responder imputation will be used for subjects with missing data at the endpoint evaluated. The last observation carried forward (LOCF) method will also be used as the sensitivity analyses for the secondary endpoints.

In general, continuous secondary efficacy variables with repeated measurements will be analyzed using a Mixed Effect Repeated Measure (MMRM) model. The mixed model includes the categorical fixed effects of treatment, Crohn's disease severity (SES-CD < 15, ≥ 15) at Baseline, week and treatment-by-week interaction and the continuous fixed covariates of baseline measurement. An unstructured variance-covariance matrix will be used. If convergence is not achieved, other variance-covariance matrix will be explored until coverage. The parameter estimations will be based on assumption of data being missing at random and using the method of restrictive maximum likelihood (REML).

Continuous secondary efficacy variables will also be analyzed using an Analysis of Covariance (ANCOVA) model including factors for treatment group and Crohn's disease severity (SES-CD < 15, ≥ 15) at Baseline, and Baseline values as a covariate. The MMRM analysis is considered primary for inferential purposes.

The additional endpoints include:

- Proportion of subjects who achieve clinical remission over time in Induction Period.
- Proportion of subjects who achieve clinical response over time in Induction Period.
- Proportion of subjects who achieve CDAI < 150 over time in Induction Period.
- Proportion of subjects with decrease in CDAI ≥ 70 points from Induction Baseline over time in Induction Period.

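### Baseline SES-CD subgroups of the co-primary endpoints can depend on outcome and dropout, because missing Baseline items are filled from the follow-up endoscopy or set to zero

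*SAP*

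**What the plan says.** The rules are in the Induction SAP, section 6.0, under SES-CD Scoring, and cover the "SES-CD score that serves as the SES-CD score for the study's efficacy analyses".

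- Item missing at Baseline but scored at follow-up: "Present at Week 12 or 16 but missing at Baseline: the missing Baseline value will be imputed based on the value given at" the follow-up visit, so that the item shows no change.
- Item missing at both visits: "Missing at both Baseline and Week 12 or 16: the missing value will be imputed as zero at both time points".
- No follow-up SES-CD at all: "If a subject only has Baseline SES-CD, and no post-Baseline SES-CD, all Baseline missing individual variables will be imputed as zero".

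The narrowing item follows the same pattern, with a cap of 2 when a more proximal segment was scored. Under Definition of Baseline for Induction Period, section 6.0 takes the latest available value up to the day of first dose. It does not reconcile this with the fill-in.

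The protocol links a missing follow-up endoscopy to dropout (synopsis, Methodology): "The Week 12 or Week 16 endoscopy will not be performed if a subject discontinues the study prior to Week 8".

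Baseline SES-CD is then used in two places:

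- **Subgroups.** Section 10.5 lists it twice for the co-primary endpoints, split at 15 and at the median. It does not say which score is meant.
- **Adjustment.** In section 10.3 categorical secondary endpoints are "analyzed using the CMH test adjusted for Crohn's disease severity" at Baseline, split at 15. The MMRM and ANCOVA carry the same factor.

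A pre-treatment version of the 15-point factor exists. Section 5.2 states: "The randomization at Baseline will be stratified by endoscopic disease severity", with the same cut.

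**The concern.** A baseline subgroup should be fixed before treatment starts. Here the score that defines it can take in a result obtained 12 or 16 weeks after randomisation, and that result also enters the co-primary endpoint of endoscopic remission. Subjects whose unscored segment is still active at follow-up gain points and may move up a category; subjects whose segment healed do not. Dropouts without a follow-up endoscopy gain nothing and count as failures under non-responder imputation. Two kinds of failure can therefore land in opposite severity groups, and a difference in effect between the groups could partly reflect the filling rule. What is at stake is the reading of the severity subgroups, not the main dose-response result.

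**Working it through.** The plan states no figure on this point, so there is none to reproduce.

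**1. Arithmetic on the rule.** Let O be the sum of the items scored at Baseline and F the follow-up value of the unscored items, with F = 0 if there is no follow-up endoscopy. The rule gives Baseline = O + F, so a subject with O below 15 enters the upper group when F ≥ 15 − O. Take O = 12 and an unscored segment truly worth 6 at Baseline (true total 18):

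| Follow-up of that segment | Filled Baseline | Group |
|---|---|---|
| Healed, F = 0 | 12 + 0 = 12 | < 15 |
| Partly healed, F = 3 | 12 + 3 = 15 | ≥ 15 |
| Unchanged, F = 6 | 12 + 6 = 18 | ≥ 15 |
| No follow-up endoscopy | 12 + 0 = 12 | < 15 |

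One pre-dose state gives two categories.

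**2. Link to the endpoint.** Endoscopic remission needs a total SES-CD of at most 4, so a remitter has F ≤ 4. If O ≤ 10, moving up needs F ≥ 5. Every such mover is therefore an endoscopic non-remitter. Only with O from 11 to 14 could a remitter move.

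**3. Size.** From the documents: remission 12% on placebo and 35% on active. Assumed, because the documents are silent: 5-30% of subjects with one unscored Baseline segment, 15% dropout in each arm with no follow-up endoscopy, remission less likely in severe disease, and an invented SES-CD distribution. One million subjects were simulated per setting, before the SES-CD ≥ 6 entry filter. The filled category is compared with one that sets missing Baseline items to zero for everyone.

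| Subjects with a missing segment | Changing category | Difference, < 15: zero-set / filled | Difference, ≥ 15: zero-set / filled |
|---|---|---|---|
| 5% | 0.5% | 25.3 / 25.5 points | 13.7 / 13.6 points |
| 10% | 1.0% | 24.8 / 25.2 | 13.7 / 13.6 |
| 20% | 2.0% | 24.8 / 25.6 | 13.7 / 13.3 |
| 30% | 3.2% | 24.5 / 25.8 | 13.8 / 13.2 |

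The shifts are 0.8 and 0.4 points at 20%, and 1.3 and 0.6 points at 30%. With complete Baseline scores the 20% setting gives 25.6 and 13.7. The filled category therefore agrees with complete scores below 15 and departs from them at 15 or more.

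At 20%, among subjects with a missing segment and an observed total below 15, 0.7% of healed, 26% of non-healed and 0% of dropouts moved up. Among all subjects with a missing segment, 49.4% on placebo and 47.5% on active were placed at 15 or more, so the category also depends slightly on treatment.

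**4. Testing.** A stratified CMH test at two-sided 0.10, with about 70 subjects in two arms, 20% missing and 5,000 runs, rejected a true null in 10.0% of runs (zero-set) and 9.9% (filled). Power was 63.7% and 63.5%.

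**5. Against sampling error.** If 45-55% of 35 subjects per arm are below 15, that subgroup has about 16 to 19 per arm. The standard error of 35% versus 12% is √[(0.35 × 0.65 + 0.12 × 0.88)/n] = √(0.3331/n). This is 14 points for n = 16 and 13 points for n = 19.

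**The case against.** A reader might infer that the adjusted secondary analyses are biased because they use the filled category. The documents do not support that. In section 6.0 the SAP puts the randomisation strata into the MMRM, the analysis that section 10.3 treats as primary for inference on continuous endpoints. Protocol 8.1.6.2.1 describes severity as a randomisation stratification variable for the CMH test, and it and the synopsis call severity a stratification variable for the ANCOVA. SAP section 4.2 drops prior anti-TNF use as a stratification factor, which also suggests that the analysis factors are the randomisation factors. Against this, section 10.3 says only severity at Baseline, and the strata cannot be carried over literally once anti-TNF use is removed and the gene-expression stratum is not listed. A programmer could use either source. That is an ambiguity, not an error.

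A reader might also infer that the co-primary test is affected. The MCP-Mod analysis in sections 10.1 and 10.2 names no severity covariate. Nor do all non-remitters move up: dropouts without an endoscopy stay in the lower group, which partly offsets the movement of active segments.

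The SAP has two safeguards. A worst-case analysis sets every missing Baseline item to zero, and SES-CD endpoints are also analysed without any missing items. Both test the endpoint; neither is said to redefine the subgroups. The subgroup point therefore stands, most clearly for the median split, which cannot come from the randomisation stratum.

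**Conclusion.** The point holds for the Baseline SES-CD subgroups of the co-primary endpoints: followed as written, the plan lets a post-randomisation result or dropout decide the category of a subject with a missing Baseline item. For the adjustment factor, the source is merely left unstated.

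The expected effect is small. Under the assumed 5-30% missingness, about 0.5-3% of subjects change category, and the subgroup differences move by at most 1.3 points, against a standard error of 13 to 14 points in the lower subgroup. No inflation of type I error was seen. These sizes rest on the assumed missingness, the equal 15% dropout and the invented score distribution; unequal dropout was not examined. The outcome dependence itself follows from the rule and needs none of these assumptions. This is a clarification worth making because it is nearly free, not a threat to the trial's conclusions.

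**What to change.** In the Induction SAP:

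1. Sections 10.3 and 10.5: state that the SES-CD factor split at 15, in the CMH, MMRM, ANCOVA and subgroup analyses, is the stratum recorded at randomisation.
2. Sections 10.5 and 7.1: state that the median split and the Baseline SES-CD summaries use pre-dose scores only, and say how an unscored item is counted.
3. Section 6.0: limit the Baseline fill-in to computing the endpoint's change from Baseline, and reconcile it with the general Baseline definition.

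The cost is a few sentences. The stratum is already held, no new data are needed, and neither the endpoint definitions nor the primary test change. If the induction tables have already been produced, the two SES-CD subgroup tables and the Baseline SES-CD summaries would need rerunning, together with any adjusted analysis that used the filled category.

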#### **5.4 Removal of Subjects from Therapy or Assessment**

##### **5.4.1 Discontinuation of Individual Subjects**

A subject may withdraw from the study at any time. The Investigator may discontinue any subject's participation for any reason, including an adverse event, safety concerns or failure to comply with the protocol.

Subjects will be withdrawn from the study immediately if any of the following occur:

- Clinically significant abnormal laboratory results or adverse events, which rule out continuation of the study medication, as determined by the Investigator and the AbbVie SDP.
- Serious infections (e.g., sepsis) which would put the subject at risk for continued participation in the trial as determined by the Investigator in consultation with the AbbVie SDP.
- The Investigator believes it is in the best interest of the subject.
- The subject requests withdrawal from the study.
- Inclusion and exclusion criteria violation was noted after the subject started study drug, when continuation of the study drug would place the subject at risk as determined by the AbbVie SDP.
- Introduction of prohibited medications or dosages when continuation of the study drug would place the subject at risk as determined by the AbbVie SDP.
- Subject is non-compliant with TB prophylaxis (if applicable) or develops active TB at any time during the study.
- The subject becomes pregnant while on study medication.

- Subject has known high grade dysplasia of the gastrointestinal tract or malignancy, except for localized non-melanoma skin cancer. Discontinuation for carcinoma in situ of the cervix is at the discretion of the Investigator.
- Subject is significantly non-compliant with study procedures which would put the subject at risk for continued participation in the trial in consultation with the AbbVie SDP.

If, during the course of study drug administration, the subject prematurely discontinues study drug use, the procedures outlined for the Week 52/ET Visit must be completed within 2 weeks of the last dose of study drug, and preferably prior to the initiation of another therapy. However, these procedures should not interfere with the initiation of any new treatments or therapeutic modalities that the Investigator feels are necessary to treat the subject's condition. Following discontinuation of the study drug, the subject will be treated in accordance with the Investigator's best clinical judgment.

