## **7.0      Protocol Deviations**

AbbVie does not allow intentional/prospective deviations from the protocol. The principal investigator is responsible for complying with all protocol requirements, and applicable global and local laws regarding protocol deviations. If a protocol deviation occurs (or is identified) after a subject has been enrolled, the principal investigator is responsible for notifying Independent Ethics Committee (IEC)/Independent Review Board (IRB) regulatory authorities (as applicable), and the following AbbVie Clinical Monitor(s):

Primary Contact:

Alternate Contact:

Such contact must be made as soon as possible to permit a review by AbbVie to determine the impact of the deviation on the subject and/or the study.

For the purposes of this protocol, reportable deviations are defined as:

- Subject entered into the study even though she/he did not satisfy entry criteria.
- Subject who developed withdrawal criteria during the study and was not withdrawn.
- Subject who received wrong treatment or incorrect dose.
- Subject who received excluded or prohibited concomitant treatment.

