A subject will be considered a failure for the efficacy analyses at a later time points after the corticosteroid dose has been increased to greater than the dose at Baseline.

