#### CIRCLE A NUMBER

## Appendix D. Crohn's Disease Activity Index (CDAI)

		Factor	Subtotal
1. Number of liquid or very soft stools (Record the frequency per day)	____ + ____ + ____ + ____ + ____ + ____ + ____ = ____ Days: 1 2 3 4 5 6 7 Sum	*	2
2. Abdominal pain rating: 0 = none, 1 = mild, 2 = moderate, 3 = severe	____ + ____ + ____ + ____ + ____ + ____ + ____ = ____ Days: 1 2 3 4 5 6 7 Sum	*	5
3. General well-being: 0 = generally well, 1 = slightly underpar, 2 = poor, 3 = very poor, 4 = terrible	____ + ____ + ____ + ____ + ____ + ____ = ____ Days: 1 2 3 4 5 6 7 Sum	*	7
4. Number of 6 listed categories the subject now has Check all items that apply:  Arthritis/arthralgia  Iritis/uveitis  Erythema nodosum/pyoderma gangrenosum/aphthous stomatitis  Fissure, abscess and/or anal fistula (draining/non-draining)  Other cutaneous fistula (draining/non-draining) Fistula  Fever over 100°F (37.8°C) during past week	_____ _____ Record "0" if no categories checked	*	20
5. Taking Lomotil/Imodium/ Loperamide/opiates for diarrhea 0 = no, 1 = yes	____	*	30
6. Abdominal mass 0 = none, 2 = questionable, 5 = defined	____	*	10
7. Hematocrit: ____	Male: (47 - hematocrit) = Female: (42 - hematocrit) = Subtotal If hematocrit > normal, enter "0"	*	6
8. Body weight: ____ (kg) Standard weight: ____ (kg)	100 * [1 - (Body wt/Standard wt)] = Percent below standard weight: ____ If body wt > std. wt, enter "0"	*	1
		Total	

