Subjects in whom the CD-related corticosteroids (systemic or rectal corticosteroids) that were not being taken at Baseline and are initiated during the study or who have equivalent dose of these medications increased to greater than the dose taken at Baseline will be censored for efficacy assessments (i.e., will be considered non-responders for categorical endpoints and will have Baseline values carried forward for non-categorical assessments) from that point through the end of the study. These subjects will continue to be evaluated in the safety population.

The equivalent steroid dose will be determined based on the table below:

| Corticosteroid | Equivalent Dose (mg) |
|--------------------|----------------------|
| Cortisone | 25 |
| Hydrocortisone | 20 |
| Prednisone | 5 |
| Prednisolone | 5 |
| Triamcinolone | 4.0 |
| Methylprednisolone | 4.0 |
| Betamethasone | 0.75 |
| Dexamethasone | 0.75 |
| Budesonide | 1 |
| Beclomethasone | 5 |
| Beclometasone | 5 |

Definition of Missing Data Imputation

The following imputation methods will be used to impute missing values in the efficacy analyses. In addition, an observed case analysis will be performed.

Non-Responder Imputation (NRI)

The NRI approach is used for binary efficacy variables. These variables can take values of 'Achieved' or 'Not Achieved' or may be missing for any reason including discontinuation from study. According to the NRI imputation approach, all missing values will be considered as 'Not Achieved.'

Last Observation Carried Forward (LOCF)

For all variables (categorical variables and continuous variables), the following rules will be used for the LOCF approach:

1. Baseline and Pre-Baseline values will not be used to impute the missing Post-Baseline values.

2. Missing values after Study Day 1 will be imputed using the latest non-missing values after Day 1 and prior to the missing value. If there are no non-missing values after Baseline, then the LOCF value will be missing.

Observed Case (OC)

Observed case analysis will be performed such that missing values will not be imputed.

However, all observed values will be replaced by Baseline value once subjects received CD-related corticosteroid therapy.

Mixed-Effect Model Repeated Measure (MMRM)

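### In induction only corticosteroid rescue is scored as failure, so a subject who starts another prohibited Crohn's therapy can still count as a remitter

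*SAP*

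**What the plan says.** **Endpoints.** Clinical remission at Week 16 is "Average daily stool frequency ≤ 1.5 and not worse than baseline AND average daily abdominal pain ≤ 1.0", with pain also not worse than baseline (Induction SAP 6.0). Endoscopic remission at Week 12/16 is SES-CD of 4 or less with "at least two point reduction versus Induction baseline and no subscore > 1 in any individual variable". Neither definition mentions concomitant medication.

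**Failure rule.** Induction SAP 6.0, CD-Related Corticosteroid Use, makes non-responders of "Subjects in whom the CD-related corticosteroids (systemic or rectal corticosteroids) that were not being taken at Baseline and are initiated during the study", and of those whose dose rises above Baseline. Protocol 8.1.3 is also limited to steroids: "A subject will be considered a failure for the efficacy analyses at a later time points after the corticosteroid dose has been increased". So is the overwrite in the observed-case analysis: "However, all observed values will be replaced by Baseline value once subjects received CD-related corticosteroid therapy".

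**Prohibited therapy.** Protocol 5.2.3.3 prohibits biologics, JAK inhibitors, azathioprine/6-MP, cyclosporine, tacrolimus, mycophenolate and rectal therapy, among others. The specific withdrawal criterion in Protocol 5.4.1 is conditional: "Introduction of prohibited medications or dosages when continuation of the study drug would place the subject at risk". Otherwise the event is a reportable deviation (Protocol 7.0): "Subject who received excluded or prohibited concomitant treatment". Induction SAP 8.0 summarises deviations, and 5.1 defines no per-protocol set.

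**Symptomatic medication.** Anti-diarrhoeals and opiates appear neither in the prohibited list nor in the stable-dose rules of Protocol 5.2.3.2. CDAI item 5 records them, with a factor of 30: "Taking Lomotil/Imodium/ Loperamide/opiates for diarrhea 0 = no, 1 = yes". Protocol 5.3.1.1 has the item answered no when an opiate is taken solely for pain.

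**The concern.** The plan already accepts that an outcome reached after rescue should not be credited to study drug. Steroid rescue is a failure in induction, and the Extension SAP (6.0, Open-Label Therapy) scores a switch to open-label ABT-494 as non-response. Other prohibited Crohn's therapies fall outside that logic, and the documents give no reason for the difference. A remission that follows a newly started biologic would enter the co-primary analysis as if it belonged to the randomised dose.

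The stool-frequency and pain endpoint has a smaller version of the same problem. The CDAI charges 30 points for anti-diarrhoeal use; the co-primary endpoint has no counterpart. Pain is half of that endpoint, yet an opiate taken only for pain is not counted even in the CDAI.

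At stake is how far an observed remission can be attributed to ABT-494. The fitted dose-response curve is meant to guide Phase 3 dose selection (Induction SAP 10.1), and few remissions are planned in the low-rate arms.

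**Working it through.** **1. What happens to each type of subject under the written rules**

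| Subject in induction | Clinical remission, Week 16 | Endoscopic remission, Week 12/16 |
|---|---|---|
| Steroid started or raised above Baseline dose | Not achieved | Not achieved if assessed afterwards |
| Other prohibited Crohn's therapy, stays to Week 16 | Scored on observed data | Scored on observed data |
| Other prohibited Crohn's therapy, leaves at Weeks 8–12 | Not achieved (Protocol 8.1.3) | Early-termination endoscopy used as the Week 12 result (Protocol 5.3.1.1) |
| New anti-diarrhoeal or opiate | Scored on observed data; both thresholds must be met | No medication rule; endpoint is the SES-CD reading |

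Non-responder imputation does not close the gap, because Induction SAP 10.2 applies it to missing values only. The sensitivity analyses there deal with missing data and discontinuation. The protocol's other non-responder rule, for study drug interruption of more than 10 days (6.1.7), is not a medication rule and does not appear in the Induction SAP.

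**2. The plan's own power figure**

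Inputs from Induction SAP 4.3: 12% on placebo, a maximum of 35% on active, 35 per group, one-sided 5%, at least 80% average MCP-Mod power over five models. The candidate-model parameters are not given, so three assumed sets were tried, each with two dose codings. Simulated average power was 0.80 to 0.83, which agrees with the stated figure.

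For orientation, a single pairwise comparison with pooled null variance:
- null SE = √(2 × 0.235 × 0.765 / 35) = 0.1014
- alternative SE = √((0.12 × 0.88 + 0.35 × 0.65) / 35) = 0.0976
- power = Φ((0.23 − 1.645 × 0.1014) / 0.0976) = Φ(0.65) = 0.74 (unpooled variance gives 0.76)

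This is not the planned test.

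**3. Scale**

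One subject is 1/35 = 2.9 points. Planned placebo remitters: 35 × 0.12 = 4.2.

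**4. Illustration on assumed rates**

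Let *u* and *v* be the shares of true non-remitters on placebo and on the best active arm whom uncounted medication moves into remission. Then p₀ = 0.12 + 0.88*u* and p₁ = 0.35 + 0.65*v*. All values of *u* and *v* are assumptions.

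| *u* / *v* | p₀ vs p₁ | Difference (points) | Pairwise power | MCP-Mod average |
|---|---|---|---|---|
| 0 / 0 | 12.0% vs 35.0% | 23.0 | 0.74 | 0.82–0.83 |
| 5% / 0 | 16.4% vs 35.0% | 18.6 | 0.56 | 0.64–0.65 |
| 5% / 5% | 16.4% vs 38.25% | 21.85 | 0.66 | 0.74–0.76 |
| 10% / 5% | 20.8% vs 38.25% | 17.45 | 0.48 | 0.56–0.57 |
| 10% / 0 | 20.8% vs 35.0% | 14.2 | 0.37 | 0.43–0.44 |
| 0 / 5% | 12.0% vs 38.25% | 26.25 | 0.82 | not run |

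MCP-Mod entries use two of the assumed parameter sets, with doses coded 0, 3, 6, 12 and 24 mg BID. The second row corresponds to 35 × 0.88 × 0.05 = 1.5 placebo subjects. The last row shows that the sign depends on which arm holds the uncounted use.

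**The case against.** The strongest reply is that the route is narrow and mostly visible. Discontinuation before Week 16 for any reason is already not achieved for clinical remission. The investigator may withdraw a subject for any reason, so the at-risk criterion is not the only way out. Early-termination procedures are preferably done before new therapy starts, which limits the Weeks 8–12 endoscopy route. Rectal and systemic steroids are already covered, and Protocol 3.0 describes conventional immunomodulators as slow in onset (3 to 6 months), so azathioprine started during induction is a weak route to remission. Concomitant medications and deviations are tabulated, so a marked imbalance would show. For permitted symptomatic drugs, counting the outcome regardless of use is a legitimate choice in a Phase 2 dose-ranging study.

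Most of this stands and limits the point. It does not remove the rule's result for a subject who starts a prohibited Crohn's therapy and stays, and a table of use does not rescore anyone.

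A reader might infer that an anti-diarrhoeal alone produces remission. The definition does not support that: average pain must also be 1.0 or less and not worse than baseline. A reader might also infer that rescue raises the placebo rate and flattens the dose-response curve. That needs more use on placebo and low doses, and the documents contain no such data.

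**Conclusion.** The concern holds as a gap in the scoring rule. Other prohibited Crohn's therapies can leave an observed remission standing on both co-primary endpoints if the subject stays to Week 16, or on endoscopic remission alone through an early-termination endoscopy at Weeks 8–12. Newly started anti-diarrhoeals and opiates can affect clinical remission only. CDAI endpoints are partly protected by item 5, except against opiates taken solely for pain.

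The size is not known from the documents. The remission rates and power values above rest on assumed fractions, and on reading the planned 12% and 35% as free of any medication effect, which the SAP does not state. They should not be read as showing that the study is underpowered; the stated average power is reproduced. More uncounted use on placebo would shrink the observed effect, and more on active arms would inflate it. The case for acting is clear attribution at low cost with few planned remitters, not a demonstrated bias.

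**What to change.** 1. **Extend the steroid failure rule** in Induction SAP 6.0. From the start date of any Protocol 5.2.3.3 therapy with potential effect on Crohn's disease, score categorical endpoints assessed afterwards as not achieved. List the classes: biologics, JAK inhibitors, azathioprine/6-MP, cyclosporine/tacrolimus/mycophenolate, and non-steroid therapeutic enemas or suppositories.
2. **Keep the primary scoring for permitted symptomatic medication and add one supplementary analysis of clinical remission.** Score as not achieved any subject whose CDAI item 5 is 1 at the assessment visit and was 0 at Baseline, or who has a newly started opiate overlapping the diary days used. The opiate criterion comes from the concomitant-medication record, because item 5 misses opiates taken only for pain.
3. **Extension SAP.** Apply both rules at each analysed visit through Week 52, relative to Induction Baseline.
4. **If induction is already locked**, label the induction analyses as supplementary. Extension SAP 3.0 places that lock in December 2016.

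Cost: SAP wording, one extra analysis and slightly lower remission rates. CDAI and concomitant medications are already collected at every treatment visit, so no new data are needed. The change affects scoring only and takes no position on which drugs patients may receive.
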